5.5.5 Physician's Assessment of Local Safety and Tolerability

Open-label phase:

Physician's assessment of local safety and tolerability will be summarised by visit.

A shift table for categories of physician's assessment of local safety and tolerability at visit 1 versus the category at visit 2 will also be done.

Maintenance phase:

Physician's assessment of local safety and tolerability when the subject is not initiating, ending or in a relapse period will be summarised by visit and by treatment group.

Physician's assessment of local safety and when the subject is initiating a relapse period will be summarised by visit and visit intervals and by treatment group.

Physician's assessment of local safety and tolerability when the subject is ending a relapse period will be summarised by visit and visit intervals and by treatment group.

A shift table for categories of physician's assessment of local safety and tolerability at start of relapse versus the category at end of relapse will also be done by visit for start of relapse and by treatment group.

Trial ID: LP0053-1004	Date: 15-JUL-2019	Version: 1.0 Page 34 of 177
-----------------------	-------------------	--------------------------------

Physician's assessment of local safety and tolerability collected when subject is in a relapse period, will be listed only.

More details for the tables and listings can be found in [Appendix I](#) and [Appendix II](#).

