3.4 Ethical Considerations

Psoriasis vulgaris is a chronic disease requiring long-term therapy for most patients. Various formulations of topical corticosteroids, topical vitamin D analogues and their combination have been shown to provide safe and effective initial therapy to achieve clearance of the lesions. However, disease signs usually recur within a few months after discontinuation of treatment in the majority of patients (28) .

LEO 90100 is a combination product of calcipotriol 50 mcg/g and betamethasone 0.5 mg/g (as dipropionate). Long-term safety of both active components of LEO 90100, used individually or in combination, has been well documented. Long-term studies of calcipotriol have shown that it is well tolerated with few adverse effects (29, 30). The local adverse effects

of calcipotriol are related to skin irritation, including burning, itching, and erythema. With the exception of skin irritation, side effects of topical calcipotriol are usually minimal; the risk of hypercalcemia/hypercalciuria is low when the drug is used appropriately.

The long-term use of products containing potent or super-potent topical corticosteroids can have a multitude of adverse cutaneous side effects, such as skin atrophy, telangiectasia, striae and tachyphylaxis. Systemic reactions due to topical use of corticosteroids are rare in adults, however, they can be severe. Adrenocortical suppression, cataract, infection, impaired glycaemic control of diabetes mellitus, and increase of intra-ocular pressure can occur, especially after long-term treatment of large areas and/or with doses exceeding recommended doses. Therefore, intermittent maintenance treatment is a commonly recommended approach for corticosteroids to control the signs of psoriasis while reducing drug exposure and thereby the risk for adverse effects (31).

LEO 90100 (calcipotriol 50 mcg/g plus betamethasone 0.5 mg/g [as dipropionate]) has proved to be a highly effective and well tolerated treatment for psoriasis vulgaris with a favourable benefit/risk profile when used for 4 and up to 12 weeks (11), but no long-term trials or investigations of the risk of skin atrophy or duration of remission and risk of rebound have been conducted.

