8.11 Other Safety Assessments

All physician's dermatologic assessments of the treatment area must be performed by a dermatologist, certified physician's assistant, advanced registered nurse practitioner or general practitioner experienced in treating psoriasis vulgaris. The same person should attempt to perform all dermatologic examinations of each individual subject.

The following assessment must be performed:

Assessment of Local Safety and Tolerability – physician and subject

The assessment of local safety and tolerability will comprise signs assessed by the (sub)investigator and symptoms reported by the subject. The signs and symptoms are not required to be reported as AEs.

At all treatment phase visits (as indicated in section 8.1), the (sub)investigator will assess application site reactions for the following signs: perilesional erythema, perilesional oedema, perilesional dryness, and perilesional erosion. The subject will assess the symptom 'application site burning or pain'.

For perilesional erythema, oedema, dryness and erosion, the area for the (sub)investigator to assess is the perilesional area, defined as the band of skin within two (2) cm from the border of the psoriatic lesion, i.e. not the lesion itself, at any given time. The assessed signs must be present in this area, but may extend beyond it in a continuous manner.

The area for the subject to assess application site burning or pain is the treatment area, including the band of skin within two (2) cm from the border of the area. The reported symptoms must be present in this area, but may extend beyond it in a continuous manner.

For each sign and symptom the highest (worst) skin reaction score across all treatment areas will be recorded by use of the following 4-point scale as specified in [Table 6](#) (Physician's assessment) and [Table 7](#) (Subject's assessment) respectively:

Table 6: Skin Reaction Scores – Physician's Assessment

	0 = absent	1 = mild	2 = moderate	3 = severe
Perilesional erythema:	No perilesional erythema	Slight, barely perceptible perilesional erythema	Distinct perilesional erythema	Marked, intense perilesional erythema
Perilesional oedema:	No perilesional oedema	Slight, barely perceptible perilesional oedema	Distinct perilesional oedema	Marked, intense perilesional oedema
Perilesional dryness:	No perilesional dryness	Slight, barely perceptible perilesional dryness	Distinct perilesional dryness	Marked, intense perilesional dryness

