9.1.1 Application site reactions: Assessment of local safety and tolerability

Application site reactions (perilesional erythema, oedema, dryness, erosion and burning and pain) which match the criteria in the Local Safety and Tolerability Scale (see Section [8.11](#)) are not to be reported as AEs in the eCRF even if they require treatment. Application site reactions other than those identified in the Local Safety and Tolerability scale must be recorded appropriately as AEs. Any application site reaction classified as SAEs must be added to the AE form in the eCRF and in addition reported to LEO on the SAE Form (according to "Investigator Reporting Responsibilities", Section [9.4.1](#)). Any treatment for an application site reaction must be recorded on the concomitant medication page of the eCRF.

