Appendix 4: Definitions of Adverse Events and Serious Adverse Events

Adverse Event Definition

An adverse event is defined as any untoward medical occurrence in a patient or clinical investigation subject administered a pharmaceutical product and which does not necessarily have a causal relationship with this treatment. An adverse event (AE) can therefore be any unfavourable and unintended sign (including an abnormal laboratory finding), symptom, or disease temporally associated with the use of a medicinal (investigational) product, whether or not related to the medicinal (investigational) product. (ICH Harmonized Tripartite Guideline for Good Clinical Practice, E6 (R1)).

This definition includes:

- accidental injuries, events related to trial procedures, reasons for any unfavourable and unplanned change in medication (drug and/or dose), clinically significant worsening of pre-existing conditions, or reasons for admission to hospital or surgical procedures unless these were planned before enrolment. It also includes AEs commonly observed and AEs anticipated based on the pharmacological effect of the investigational product. In addition, any laboratory abnormality assessed as clinically significant by the (sub)investigator must be recorded as an AE.

Serious Adverse Event Definition

A serious adverse event (SAE) is any untoward medical occurrence that

- results in death
- is life-threatening
- requires inpatient hospitalisation or prolongation of existing hospitalisation. Planned hospitalisation or planned prolonged hospitalisation do not fulfill the criteria for being an SAE but should be documented in the subject's medical record.
- results in persistent or significant disability/incapacity
- is a congenital anomaly/birth defect

or

- is a medically important condition. Events that may not be immediately life-threatening or result in death or hospitalisation but may jeopardise the subject or may require intervention to prevent one of the other outcomes listed in the definition above. Examples are intensive treatment in an emergency room or at home for allergic broncospasm, blood dyscrasias and convulsions that do not result in hospitalization, development of drug dependency or drug abuse.

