5.5.6 Subject's Assessment of Local Safety and Tolerability

Open-label phase:

Subject's assessment of local safety and will be summarised by visit. A shift table for categories of subject's assessment of local safety and tolerability at visit 1 versus the category at visit 2 will also be done.

Maintenance phase:

Subject's assessment of local safety and tolerability collected when the subject is not initiating, ending or in a relapse period will be summarised by visit and by treatment group.

Subject's assessment of local safety and tolerability collected when the subject is initiating a relapse period will be summarised by visit and visit intervals and by treatment group.

Subject's assessment of local safety and tolerability collected when the subject is ending a relapse period will be summarised by visit and visit intervals and by treatment group.

A shift table for categories of subject's assessment of local safety and tolerability at start of relapse versus the category at end of relapse will also be done by visit for start of relapse and by treatment group.

Subject's assessment of local safety and tolerability collected when the subject is in a relapse period, will be listed only.

More details for the tables and listings can be found in [Appendix I](#) and [Appendix II](#).

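### Non-serious local reactions on the tolerability scale stay off the AE form, and their maintenance-phase tables omit mid-rescue scores, have no place for early-withdrawal scores and give no incidence by arm

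*SAP*

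**What the plan says.** **Reporting rule.** Protocol 9.1.1 says that application site reactions matching the tolerability scale "are not to be reported as AEs in the eCRF even if they require treatment". There are two safeguards: "Any application site reaction classified as SAEs must be added to the AE form in the eCRF", and "Any treatment for an application site reaction must be recorded on the concomitant medication page of the eCRF". Protocol 8.11 is softer: "The signs and symptoms are not required to be reported as AEs". Section 8.14 repeats that softer form. Appendix 4 defines AEs broadly enough to take in the reason for an unplanned, unfavourable change of medication.

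**Known effect.** Protocol 3.4 states that the local adverse effects "of calcipotriol are related to skin irritation, including burning, itching, and erythema".

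**Planned analysis.** Protocol 11.3.6.3 has all five items summarised over time, by treatment group in the maintenance phase, without regard to relapse status. The SAP divides maintenance-phase scores into visits unrelated to relapse, start of relapse and end of relapse, and adds a start-to-end shift table. For the rest, 5.5.5 says "Physician's assessment of local safety and tolerability collected when subject is in a relapse period, will be listed only" and 5.5.6 says "Subject's assessment of local safety and tolerability collected when the subject is in a relapse period, will be listed only". Shells 70 and 76, the tables unrelated to relapse, run from Visit 2 to Visit 15.

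**The concern.** Local tolerability is a named safety assessment (Protocol 5.3) under a long-term safety objective. A non-serious burning or erythema score that matches the scale cannot enter the AE counts, AE rates or AE-withdrawal summaries. Whatever the tolerability tables omit is therefore not tabulated anywhere.

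The tables also report prevalence at each visit among subjects still attending and not in relapse. The SAP recognises the weakness of that kind of summary elsewhere. Section 5.7 drops by-visit summaries of m-PASI, DLQI and other measures because those who remain are a selected group. Section 5.5.3 drops the AE tests because withdrawal may differ between arms. Tolerability is open to the same selection, and a subject who leaves because of irritation is the one most likely to be missed. A reader of the report could not say what proportion of each arm ever had a moderate or severe reaction.

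**Working it through.** The documents give no figure on this point, so there is none to reproduce. The check sets the text against the table shells and counts visits.

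**1. Which on-rescue scores are tabulated.** SAP Table 1 ends the relapse period before the visit that stops rescue, so that visit's score counts as end of relapse and is tabulated (Shells 72 and 78).
- Relapse confirmed at a scheduled visit (Protocol 6.1.4.1): the next visit is four weeks later and ends rescue. Mid-course scores: 0. End scores: 1.
- Relapse confirmed at an unscheduled visit (Protocol 6.1.4.2): this needs more than 7 days to the next regular visit. With nominal 28-day intervals, rescue starts on day d = 1 to 20, and the regular visit falls on rescue day 28 − d = 8 to 27. Mid-course scores: 1, listed only. End scores: 1, tabulated.

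**2. Share listed only.** Let u be the share of relapses confirmed at unscheduled visits. Each course gives one end score and, on average, u mid-course scores, so the listed-only share of on-rescue scores is u/(1 + u). The documents do not give u.

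| u (assumed) | u/(1 + u) |
|---|---|
| 0 | 0% |
| 0.25 | 0.25/1.25 = 20% |
| 0.50 | 0.50/1.50 = 33% |
| 1 | 1/2 = 50% |

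**3. Early withdrawal.** Protocol Table 4 schedules both assessments at the early-withdrawal visit. Shells 70 and 76 have no row for it, and the SAP has no rule assigning the score to a numbered visit. Other safety data are treated explicitly: SAP 5.5.8 and 5.5.9 add tables for discontinuing subjects, and 5.5.7 says early-termination ACTH results are listed only. At the 30% drop-out assumed in Protocol 11.1, subjects without a Visit 15 score would number 0.30 × 380 = 114 as planned. For the 545 randomised in SAP Table 8 (132 + 55 + 52 + 68 + 56 + 68 + 114), the number is 0.30 × 545 = 163.5, about 164. Both are upper bounds on the scores affected. Subjects who exit after failed rescue fall in the end-of-relapse tables, and subjects lost to follow-up have no withdrawal score to place.

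**4. Incidence.** No table in SAP Appendix I counts subjects by worst post-randomisation score.

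**5. Documentation.** SAP 5.7 lists changes from the protocol analyses. The departure from 11.3.6.3 is not among them.

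**The case against.** The strongest reply is that most of what matters is already shown. The score after four weeks of daily rescue is tabulated by arm and shifted against the start of the course. Visit 2, after four weeks of daily open-label use, is tabulated and shifted for the whole open-label safety set. Rescue is active LEO 90100 in both arms, so the randomised contrast in tolerability lies mainly in the table of visits unrelated to relapse, which is kept. Every individual score is in Listings 7-7 and 7-8, and withdrawal reasons are tabulated. The scale covers perilesional signs and burning or pain only. Itching is not on it, so 9.1.1 still requires itching to be recorded as an AE. A missing row in a template shell is an ambiguity rather than a declared exclusion.

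All of this stands, and it rules out two stronger readings. A reader might infer that irritation during daily rescue appears in no table. The end-of-relapse tables contradict that, and at the assumed 25-50% they hold 67-80% of on-rescue scores. A reader might also infer that the product's irritant harm is shown to be under-reported. The documents do not show this: the items are solicited on a graded scale at every treatment-phase visit, serious reactions go on the AE form, and treatment is recorded as concomitant medication.

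None of it supplies incidence by arm, tabulates the mid-course scores, or says where the score of a subject who withdraws outside a relapse period belongs.

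**Conclusion.** The point holds as a gap in the tabulation of local tolerability, and it is cheap to close. Non-serious reactions matching the scale are summarised only in the tolerability tables. In the maintenance phase those tables omit mid-course rescue scores: 20-33% of on-rescue scores if 25-50% of relapses are confirmed at unscheduled visits, with nominal visit timing, and at most 50% under any value of u. They have no defined place for early-withdrawal scores of subjects who leave outside a relapse period; these number fewer than about 114 of 380, or 164 of 545, at 30% drop-out. They give no subject-level incidence by arm. The departure from Protocol 11.3.6.3 is not recorded.

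The effect on the tolerability conclusion is a risk whose size cannot be found from the documents. The differing statements in Protocol 9.1.1, 8.11, 8.14 and Appendix 4 are an inconsistency to be resolved. They do not by themselves establish which reporting rule should apply.

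**What to change.** Before unblinding, in SAP 5.5.5 and 5.5.6:

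1. Add one table by arm giving the number and percentage of subjects by worst post-randomisation score for each sign and symptom. It should cover all visits (scheduled, unscheduled, during relapse and early withdrawal), with a split for visits on rescue.
2. Add an early-withdrawal row to Shells 70 and 76, and a during-relapse summary beside the start- and end-of-relapse tables.
3. Record the departure from Protocol 11.3.6.3, and its reason, in SAP 5.7.

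Separately, reconcile Protocol 9.1.1 with 8.11, 8.14 and Appendix 4, so that one statement says whether and when reactions on the scale are recorded as AEs. The SAP is dated July 2019 and follows blind review, so this may come too late to change data collection. In that case the report should state the rule that sites actually followed.

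The cost is two or three extra tables from data already collected. No new assessment is needed, and no efficacy analysis changes.

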5.5.6 Subject's Assessment of Local Safety and Tolerability

Open-label phase:

Subject's assessment of local safety and will be summarised by visit. A shift table for categories of subject's assessment of local safety and tolerability at visit 1 versus the category at visit 2 will also be done.

Maintenance phase:

Subject's assessment of local safety and tolerability collected when the subject is not initiating, ending or in a relapse period will be summarised by visit and by treatment group.

Subject's assessment of local safety and tolerability collected when the subject is initiating a relapse period will be summarised by visit and visit intervals and by treatment group.

Subject's assessment of local safety and tolerability collected when the subject is ending a relapse period will be summarised by visit and visit intervals and by treatment group.

A shift table for categories of subject's assessment of local safety and tolerability at start of relapse versus the category at end of relapse will also be done by visit for start of relapse and by treatment group.

Subject's assessment of local safety and tolerability collected when the subject is in a relapse period, will be listed only.

More details for the tables and listings can be found in [Appendix I](#) and [Appendix II](#).

5.5.7 ACTH-Challenge Test

Open-label phase:

For the group of subjects undergoing the ACTH-challenge test, the number and percentages of subjects with serum-cortisol concentration values ≤ 18 mcg/dl at 30 minutes and 60 minutes after the ACTH-challenge test will be summarised by visit.

The serum-cortisol concentration at time 0 (just before the ACTH-challenge test) and at 30 and 60 minutes after ACTH-challenge at visit 1 and visit 2 will be summarised.

Trial ID: LP0053-1004	Date: 15-JUL-2019	Version: 1.0 Page 35 of 177
-----------------------	-------------------	--------------------------------

Individual data for subjects with serum cortisol concentration values ≤ 18 mcg/dl at either 30 or at 60 minutes after ACTH-challenge in the open-label phase will be tabulated.

A mean plot of the serum-cortisol concentration at time 0, and at 30 and 60 minutes after the ACTH-challenge test for visit 1 and visit 2 will be done.

Maintenance phase:

The number and percentages of subjects with serum-cortisol concentration values ≤ 18 mcg/dl at 30 minutes and 60 minutes after the ACTH-challenge test will be summarised by visit and by treatment group.

The serum-cortisol concentration at time 0 and at 30 and 60 minutes after ACTH-challenge tests will be summarised by visit and treatment group.

Individual data for subjects with serum cortisol concentration values ≤ 18 mcg/dl at either 30 or at 60 minutes after ACTH-challenge will be tabulated.

A mean plot of the serum-cortisol concentration at time 0, and at 30 and 60 minutes after the ACTH-challenge test by treatment group will be done.

Results from ACTH-tests performed at early termination visits will be listed only and are not included in the above-mentioned tables and figures.

More details for the tables and listings can be found in [Appendix I](#) and [Appendix II](#).

